1.0 Study Summary

| | |
|---|--|
| Study Title | Dopaminergic Therapy for Inflammation-Related Anhedonia in Depression |
| Study Design | 6-week randomized, double-blind, placebo-controlled crossover |
| Primary Objective | To determine a daily dosing strategy for the dopamine precursor, levodopa (L-DOPA), that will increase functional connectivity (FC) in ventral striatum to ventromedial prefrontal cortex (VS-vmPFC) reward circuitry in major depressive disorder (MDD) patients with high inflammation and anhedonia. |
| Secondary Objective(s) | Data regarding safety and tolerability, and preliminary data on the potential for L-DOPA to improve anhedonia and motivation will also be collected. Additional behavioral, biologic and MRI measures (at baseline) will be collected for use as predictors of response and to enhance interpretation of results. |
| Research Intervention(s)/Interactions | L-DOPA; placebo |
| Study Population | Medically stable and medication-free adults (ages 25-55) with Major Depressive Disorder, plasma CRP >2 mg/L, and high anhedonia (score >/=2 on the anhedonia question of Patient Health Questionnaire [PHQ]-9) |
| Sample Size | 35 |
| Study Duration for individual participants | >8 Visits; ~8 week duration |
| Study Specific Abbreviations/ Definitions | Levodopa (L-DOPA) Major depressive disorder (MDD) Functional connectivity (FC) C-reactive protein (CRP) Ventral striatum to ventromedial prefrontal cortex (VS-vmPFC) |
| Funding Source (if any) | NIMH R61 Grant (R61MH121625) |

2.0 Objectives

The primary objective of the proposed research is to determine a daily dosing strategy for the dopamine precursor, levodopa (L-DOPA), that will increase

functional connectivity (FC) in ventral striatum to ventromedial prefrontal cortex (VS-vmPFC) reward circuitry in major depressive disorder (MDD) patients with high inflammation and anhedonia. More than 30% of patients with MDD fail to achieve remission with conventional antidepressants and even responders exhibit significant residual symptoms including anhedonia. Inflammation is elevated in a significant portion of patients with MDD, particularly in those patients who are resistant to conventional antidepressant therapies. Preclinical and clinical findings indicate that inflammation can affect striatal dopamine availability and release, to contribute to symptoms of anhedonia and reduced motivation. We have previously reported a relationship between inflammation and FC in dopaminergic reward circuitry in patients with MDD whereby patients with increased inflammation, as defined by plasma C-reactive protein (CRP), exhibited lower VS-vmPFC FC. This VS-vmPFC FC was in turn correlated with symptoms of anhedonia. Clinical and translational evidence from our group and others suggests that inflammation impacts corticostriatal circuits by decreasing the synthesis and availability of dopamine. Our preliminary data demonstrate that VS-vmPFC FC connectivity was increased after acute administration of L-DOPA compared to placebo in patients

with high CRP (indexed as CRP >2 mg/L), indicating that increasing dopamine with L-DOPA can reverse the impact of inflammation on this circuit. The dopamine precursor, L-DOPA, is taken up in the brain and rapidly converted to dopamine by DOPA decarboxylase. Despite evidence of reduced dopamine availability in MDD, little work has explored the potential for L-DOPA to improve anhedonia and motivation in MDD. By building on our previous work demonstrating a functional link between decreased dopamine availability and impaired FC in reward circuits of MDD patients with high inflammation, this study will test the hypothesis that treatment with L-DOPA will improve depressive symptoms in MDD patients with high inflammation and anhedonia by increasing FC in reward circuitry and improving motivation.

In order to obtain 30 study completers (~10-15% expected attrition rate), 35 medication-free, medically-stable and otherwise psychiatrically healthy adults (25-55 yrs) with 1) current MDD per DSM-V criteria, 2) plasma CRP >2 mg/L, and 3) score ≥ 5 on an anhedonia subscale of the Inventory of Depressive Symptomatology-Self-Report (IDS-SR), will be randomized to two study tracks (A and B) to receive both placebo and L-DOPA (starting dose of 150 mg/day with dose escalation 150 mg/day per week to a final dose of 450 mg/day) in a 6-week, double-blind, placebo-controlled, crossover study (see **Figure 1**). Patients will undergo resting-state functional magnetic resonance imaging (fMRI) at baseline, after 1-week of placebo, and after 1-week at each dose of L-DOPA to establish target engagement in the brain for L-DOPA versus placebo to improve FC in reward circuitry. Symptoms of anhedonia and an objective measure of motivation will be assessed as preliminary data regarding L-DOPA effects on behavior in relation to change in FC. Additional behavioral, biologic and MRI measures will be collected at baseline for use as predictors of response and to enhance interpretation of results. Safety and tolerability and data on the effect of L-DOPA on anhedonia and motivation in relation to target engagement in the brain (FC) will also be assessed.

Aim 1: To determine whether L-DOPA increases VS-vmPFC functional connectivity in MDD patients with high CRP (>2 mg/L) and anhedonia.

Hypothesis 1: L-DOPA versus placebo will increase VS-vmPFC FC along with plasma L-DOPA levels, and with maximal effects at higher doses.

Exploratory aims: To obtain information on the dosing and tolerability of L-DOPA in our patient population, while collecting preliminary data on whether L-DOPA-sensitive fMRI FC brain biomarkers are affected in association with improvement in anhedonia and motivation.

Exploratory hypotheses: L-DOPA will be well-tolerated in otherwise medically-stable MDD adults with CRP >2mg/L and anhedonia at all doses tested, and improvement in FC in reward circuitry will occur in association with improved motivation and motor slowing.

3.0 Background

[figure not shown]
Depression is common, affecting ~10 million in the US alone, and confers a personal and societal burden. More than 30% of patients with major depressive disorder (MDD) fail to achieve remission with conventional antidepressants, and even responders exhibit significant residual symptoms including anhedonia.¹⁻⁴ Therefore, new conceptual frameworks are needed to reveal pathophysiologic pathways and neurobiological targets for development of novel treatments for subgroups of MDD patients who are not sufficiently responsive to existing therapies. Relevant in this regard, one pathophysiologic pathway thought to contribute to symptoms of depression and particularly anhedonia is inflammation.⁵⁻⁷ A significant proportion of patients with MDD are reliably found to exhibit increased inflammatory markers in both the periphery and central nervous system, as measured by inflammatory cytokines and acute phase reactants such as C-reactive protein (CRP).⁸⁻¹¹

Elevated CRP and other peripheral blood markers of inflammation have also been found to predict future development of depressive symptoms,¹²⁻¹⁴ and patients with high levels of inflammatory markers are more resistant to standard antidepressants such as selective serotonin reuptake inhibitors (SSRIs).^{5,15-19}

Working Model and Study

Overview. Administration of inflammatory stimuli or cytokines to laboratory animals and humans affects reward pathways in the brain to lead to anhedonia and reduced motivation, which has been shown to be mediated by reduced synthesis and availability of striatal dopamine.²⁰⁻²⁵ We recently reported a relationship between increased inflammation (as defined by plasma CRP) and low functional connectivity between the ventral striatum (VS) and ventromedial prefrontal cortex (vmPFC), key structures that receive mesolimbic dopamine input,²⁶ in patients with MDD, in association with increased anhedonia.²⁷ Furthermore, our preliminary results also indicate that VS-vmPFC FC in MDD patients can be increased by acute administration of the dopamine precursor levodopa (L-DOPA) in association with improved motivation, but only in patients with high inflammation. Together these findings indicate that MDD patients with high inflammation have low striatal dopamine availability that drives decreased FC in reward circuitry and increased anhedonia/reduced motivation (**Figure 2A**).⁷ These data also support our hypothesis that VS-vmPFC FC in these patients can be strengthened by L-DOPA administration to lead to reduced anhedonia and improved motivation (**Figure 2B**).

This study will determine a daily dosing strategy for L-DOPA that will increase FC in VS-vmPFC reward circuitry in a 6-week randomized, double-blind, placebo-controlled, crossover study with 3 doses of L-DOPA in the R61. Data regarding the potential for L-DOPA to improve anhedonia

BH4-tetrahydrobiopterin; CRP-C-reactive protein; DDC-dopadecarboxylase; FC-functional connectivity; L-DOPA- levodopa; Phe-phenylalanine; PH-Phehydroxylase; ROS-reactive oxygen species; Tyr-tyrosine; TH-Tyrosinehydroxylase; vmPFC- ventromedial prefrontal cortex; VS-vmPFC FC.

and motivation will also be collected. Milestones for R61: To establish target engagement in the brain, we expect that at least one of 3 doses of L-DOPA will produce a mean increase in VS-vmPFC FC that is $\geq 20\%$ higher than that of placebo.

This study aims to address an unmet need to investigate novel therapeutic strategies that may be targeted to sub-populations of patients with MDD based on a known pathophysiology that can be identified by a combination of peripheral blood and behavioral biomarkers. Despite evidence of low dopamine function in MDD,^{3,28,29} the ability of existing dopaminergic therapies with well-characterized pharmacology, like L-DOPA, to affect brain circuits in MDD has yet to be explored. Further novelty and innovation exist in targeting such therapies to MDD patients with high inflammation and anhedonia, a population frequently reported-on but understudied in experimental medicine or clinical trials. The choice of L-DOPA for this study is particularly well-matched to this target population as inflammation is known to impede dopamine synthesis (see **Figure 2**), which is rapidly increased by the dopamine precursor, L-DOPA. Therefore, this work involving a dopamine agonist with known pharmacology will not only test a potential new therapy³⁰ but will also provide the foundation for the development of novel dopaminergic therapies for the ~30-50% of MDD patients with high inflammation^{19,31-35} who are less responsive to conventional antidepressants like SSRIs.^{5,15-19}

Inflammation Impacts Reward Circuitry through Decreased Dopamine Synthesis and Availability. Numerous neuroimaging studies in subjects peripherally administered cytokines or other inflammatory stimuli (either as clinical therapy or in laboratory experiments) have found that inflammation preferentially affects corticostriatal circuitry that is relevant to anhedonia and motivation, as well as psychomotor speed.^{21,22,36-39} For example, functional magnetic resonance imaging (fMRI) has demonstrated decreased ventral striatal neural activation to hedonic reward in patients administered the inflammatory cytokine interferon (IFN)- α to treat hepatitis C, which correlated with reduced motivation and activity.²¹ Typhoid vaccination and endotoxin administered in the laboratory to healthy subjects produced similar effects on the basal ganglia, including decreased neural activation of the ventral striatum to hedonic reward and decreased corticostriatal FC, which also correlated with symptoms of anhedonia and psychomotor slowing.^{22,38-40} Positron emission tomography (PET) neuroimaging investigating cytokine effects on dopamine metabolism revealed increased uptake and decreased turnover (indirect measures of dopamine capacity and release) of radiolabeled L-DOPA, [¹⁸F]fluorodopa, in the caudate, putamen, and ventral striatum of IFN- α -treated patients.²¹ Our translational work in non-human primates and studies in rodents have directly linked the effects of inflammation on corticostriatal reward circuits to decreased availability and release of striatal dopamine.^{20,24,41,42} Indeed, we conducted in vivo microdialysis and PET neuroimaging with [¹¹C]raclopride displacement following amphetamine challenge in IFN- α -treated monkeys.²⁰ Results indicated that stimulated dopamine release was decreased in the striatum (including nucleus accumbens) after chronic administration of IFN- α , and decreased dopamine release, as measured by in vivo microdialysis, was correlated with reduced effort-based sucrose consumption.²⁰ A primary pathway by which inflammation impacts dopamine is by decreasing the availability of tetrahydrobiopterin (BH4), an enzyme co-factor required for synthesis of dopamine via the conversion of phenylalanine to tyrosine and tyrosine to L-DOPA (see **Figure 1**).⁴³ We and others have observed evidence of reduced BH4 activity in patients administered IFN- α , which correlated with decreased cerebrospinal concentrations of dopamine and increased depressive symptoms.^{23,44} To examine whether inflammation reduces availability of dopamine by depleting dopamine precursors, we administered L-DOPA via reverse in vivo microdialysis to monkeys treated with chronic IFN- α , and the inflammation-induced reductions in striatal dopamine release were restored by L-DOPA.²⁴ Therefore, pharmacological agents that improve dopamine synthesis may effectively treat anhedonia and reduced motivation in MDD patients with high inflammation.

Pharmacology of L-DOPA and Potential to Improve Reward Circuit Function, Motivation and Anhedonia in Depression with High Inflammation. Unlike dopamine itself, L-DOPA crosses the blood-brain-barrier (BBB) and is rapidly converted to dopamine by DOPA

decarboxylase (DDC) then packaged and either stored or released from presynaptic dopaminergic terminals. L-DOPA is currently used in combination with carbidopa (which does not cross the BBB) to increase dopamine transmission in dopamine-deficient patients with Parkinson's disease (PD) or dopamine-mediated sleep movement disorders like restless legs syndrome (RLS).^{45,46} Carbidopa blocks the conversion of L-DOPA to dopamine in the periphery, allowing more L-DOPA to be taken up by the brain and to reduce peripheral side effects from dopamine receptor activation. In addition to having known pharmacology, the pharmacokinetics of L-DOPA and its effects on brain dopamine are well established.^{24,47} Despite evidence of reduced dopamine availability in depression,²⁴ little work has explored the potential for dopaminergic therapies like L-DOPA to improve anhedonia and motivation in MDD. Case series beginning in the 1960s report improved depressive symptoms with L-DOPA monotherapy or augmentation, particularly in patients considered to have a slowed or "retarded" phenotype of depression.⁴⁸⁻⁵¹ In new onset PD, L-DOPA was shown to improve symptoms in 28 out of 31 patients with a mean decrease in the Hamilton Depression Rating Scale (HAM-D) of 11.7,⁵² whereas others have reported beneficial effects on depressive symptoms, quality of life and/or cognitive performance.⁵³⁻⁵⁵ With regard to hedonic tone and motivation, L-DOPA increased the frequency by which healthy subjects chose high-probability gains in an instrumental learning task.⁵⁶ Similarly, L-DOPA selectively improved motivation for (wanting), versus sensitivity for (liking) or learning about, reward in mice with a genetic depletion of dopamine.⁵⁷ These findings support the hypothesis that L-DOPA is able to improve motivation, particularly in subjects with low dopamine synthesis and availability. Agents that increase dopamine signaling, such as the dopamine receptor agonist pramipexole, have demonstrated efficacy in treatment-resistant depression,^{58,59} and MDD patients with moderately increased CRP (≥ 1 mg/L) were found to exhibit a robust response to the combination of a SSRI plus bupropion (an antidepressant with stimulant properties) compared to a poor response to the SSRI alone.¹⁹ These findings provide support for our hypothesis that MDD patients with high inflammation, who are often resistant to SSRIs, may be especially responsive to dopaminergic therapies. However, dopamine receptor agonists bind to receptors for other systems such as serotonin,⁶⁰ and bupropion is not specific for the dopamine transporter.⁶¹ Furthermore, inflammation is thought to decrease dopamine neurotransmission by interfering with rate-limiting aspects of dopamine synthesis that occur upstream of the conversion of L-DOPA to dopamine by DDC. Thus, L-DOPA is the most direct and specific pharmacological approach to increase dopamine transmission and improve corticostriatal reward circuits in association with behavior in MDD patients with high inflammation who may exhibit a fundamental depletion of dopamine availability. Accordingly, L-DOPA is the most appropriate compound for the R61/R33 mechanism as it is 1) well-matched to the underlying mechanism and 2) will isolate a specific dopaminergic effect in the target population, which will have implications for development of novel therapeutics, or the targeting of existing compounds like bupropion,^{19,62} pramipexole⁵⁸ or even L-DOPAf³⁰ (as will be explored in the R33) to patients with MDD, high inflammation and anhedonia. The R33 can then inform future studies that examine L-DOPA as a monotherapy or adjunct and compare the response to other dopaminergic therapies (or SSRIs) and in low CRP patients.

4.0 Study Endpoints *

Milestone for R61: Target Engagement of Brain. Targeted VS-vmPFC connectivity will serve as the primary outcome and will be assessed for determining the Go/No-Go Criteria. Targeted FC for each subject and treatment condition will be calculated as the degree of correlation in activity between a 3mm³ radius sphere in VS^{27,65} and the vmPFC ROI identified as being reward-sensitive in neuroimaging meta-analyses¹⁰⁵ (MNI coordinates x=0, y=44, z=-8, cluster size=1408 mm³ and encompassing parts of BA11 and ventral BA32 of ACC) or other similar ROIs used to define vmPFC in our previous work.^{27,64,65,106} This method will ensure rigor and reproducibility and application of results to potential future trials because the seeds and ROI are predefined, as opposed to those derived from whole-brain and data-driven analyses which are determined based on the specific patient sample. Z-scores will be extracted and the change in mean FC values after each dose of L-DOPA or placebo compared to baseline will be calculated.

FC between bilateral VS seeds and the vmPFC ROI will be examined separately and change in FC in either the right or left VS can contribute to meeting the Go/No-Go criteria. However, based on our previous work in MDD and IFN- α -induced depression^{21,27} and our preliminary studies, we anticipate that this change will be more pronounced on the left side. Response may also be strongest in subjects with greatest bioavailability of L-DOPA. If more than 1 dose of L-DOPA meets criteria, % of patients and mean number of reported side effects will be compared across doses to determine the effective dose that was most tolerated by patients. If doses are similarly tolerated, % change in behavior (EEfRT > anhedonia) will be used. Statistical significance, ES or sensitivity analyses may be used to assist with selection of the optimal dose.

Additional Analyses for Publication and Dissemination: Brain Target- Targeted FC Z scores (as described above) will be entered into linear regression models including clinical covariates (see below) and both conservative (Bonferroni) and powerful (Fisher LSD) post-hoc analyses to assess change in FC across the 3 doses of L-DOPA compared to placebo and to each other. Linear models will also be used to determine whether FC increases as a function of increasing plasma L-DOPA, and whether patients with low bioavailability exhibit low Δ FC. In addition to the targeted FC that will be used to assess Go/No-Go criteria, hypothesis-driven and data-driven whole-brain analysis will also be explored and compared before and after L-DOPA and placebo. Consistent with our previous data, these analyses will include VS seed-to-voxel-wise comparisons of L-DOPA versus placebo, as well as network analyses using GBC and PBNA, as a secondary outcome measure and to identify other circuits that may be affected by L-DOPA. For all analyses, concentration of CRP and final dose will be explored as a linear predictor of response to L-DOPA. Clinical covariates such as age, sex, race, BMI and ATQR and/or bipolarity scores will be explored as potential confounders or moderators of L-DOPA effects on FC. **Integration of Brain and Behavior:** As described for FC, linear regression models and post-hoc analyses will be used to assess change in behavioral outcomes across the 3 doses of L-DOPA compared to baseline, to placebo and to each other, and whether response was modified by plasma bioavailability of L-DOPA, CRP, cytokine or sex hormone concentrations, or clinical covariates. Random intercept linear mixed models will be used to assess whether change in FC predicts change in anhedonia and motivation and in relation to clinical covariates. Overall depression scores and SHAPS-C and MAP-SR will be explored as secondary outcomes. Summary scores for dose-response (e.g. AUC) may be used to assess relationships among variables.

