Reaction Time Task (CANTAB): The reaction time test includes simple and choice reaction time tasks and is divided into 5 stages requiring increasingly complex chains of responses and providing distinction between reaction (or decision) time and movement latencies (3).

Trail Making Tests A (TMT): is a commonly used neuropsychological measure with updated norms. Part A (TMT-A) requires the patient to connect numbered circles in order and reflects a measure of basic attention and processing speed.

Digit Symbol Task (DSST): The Digit Symbol Substitution Task is a subtest of the Wechsler Adult Intelligence Scale (WAIS) and consists of rows of blank squares, each printed with a randomly assigned number. The test involves graphimotor speed, visual scanning and memory, with about half of the variance being accounted for by graphimotor speed, a third by visual scanning and 4-5% by memory.

Safety and Tolerance

Adverse Event Recording: All adverse events will be coded in standard MeDRA terms (Version 14.1), and whether events are expected and study-related will be determined by the study PI or designee. In addition, severity and start and end dates will be recorded as well as any evidence of unanticipated problems. This information will be provided to the Department of Psychiatry and Behavioral Sciences DSMB and IRB annually as described in the Human Subjects Section.

6.3 Protection Against Risk:

Every effort will be taken to prevent injury or distress that may result from this study.

Recruitment and Informed Consent:

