Target Engagement in the Brain for R61 Go/No-Go Criteria: Targeted VS-vmPFC connectivity will serve as the primary outcome and will be assessed for determining the Go/No-Go Criteria. Targeted fMRI FC will be calculated as the degree of correlation in activity using an a priori defined seed in VS and region of interest (ROI) in vmPFC (per the literature and our previous studies). This method will ensure rigor and reproducibility and application of results to potential future trials because the seeds and ROI cluster are predefined as opposed to those derived from whole-brain and data-driven analyses which are determined based on the specific patient sample. FC Z-scores will be extracted and the change in mean FC values after each dose of L-DOPA or placebo compared to baseline will be assessed. We expect that at least one dose of L-DOPA will increase VS-vmPFC FC by $\geq 20\%$ greater than placebo. If more than 1 dose of L-DOPA is able to engage the FC outcome at the proposed thresholds, the percent of patients and mean number of reported side effects will be compared across doses to determine the effective dose that was most tolerated by patients. If doses are similarly tolerated, the one with greatest impact on behavior (% change in behavior, EEfRT > anhedonia), or lowest dose meeting all of the above criteria, will be chosen. Statistical significance, ES or sensitivity analyses may be used to assist with selection of the optimal target dose of L-DOPA for the R33 phase.

Additional Analyses for Publication and Scientific Dissemination:

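### The hypothesis that L-DOPA is well tolerated at all doses has no analysis of its own: the only written side-effect comparison is a conditional dose-selection step that uses neither placebo nor recorded severity

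*Combined protocol and SAP*

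**What the plan says.** Section 2.0 lists as an exploratory hypothesis that "L-DOPA will be well-tolerated in otherwise medically-stable MDD adults with CRP >2mg/L and anhedonia at all doses tested". Section 1.0 places the topic among the secondary objectives: "Data regarding safety and tolerability, and preliminary data on the potential for L-DOPA to improve anhedonia and motivation will also be collected". Section 2.0 also has a sentence that begins "Safety and tolerability and data on the effect of L-DOPA on anhedonia and motivation" and ends by saying that these will be assessed. None of these places names a summary measure, a comparator or a criterion for good tolerability.

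The analysis text has one side-effect comparison. Section 4.0 (Milestone for R61) reads: "If more than 1 dose of L-DOPA meets criteria, % of patients and mean number of reported side effects will be compared across doses". Section 17.1 repeats the condition and gives the purpose: "mean number of reported side effects will be compared across doses to determine the effective dose that was most tolerated by patients". Neither mentions placebo or severity.

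The data would support more. Under Safety and Tolerance, section 6.2 says of adverse events that "severity and start and end dates will be recorded as well as any evidence of unanticipated problems". Table 2 schedules adverse events and the dyskinesia review at every treatment visit, whichever treatment the patient is on. Vital signs at weeks 2 and 5 are taken only if the visit is in person (section 6.1). The additional analyses in sections 4.0 and 17.1 compare FC and behaviour with placebo. They contain no side-effect analysis.

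**The concern.** A hypothesis about all doses is served only by a step that covers the doses passing an imaging threshold, and only when two or more pass. Even when it runs, it yields L-DOPA rates without a background rate. Table 1 lists insomnia, headache, dizziness and drowsiness as anticipated. Such symptoms may also be present in depressed patients on placebo, and the placebo period is the trial's own measure of how often. A count of reports also gives a mild and a severe event equal weight. What is at stake is whether the trial can say anything interpretable about tolerability, which the plan also uses as the first criterion for choosing among passing doses for the R33 phase.

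**Working it through.** **1. Is there a figure to reproduce?** No. The documents give no sample size, margin or threshold for tolerability. The FC inputs used below are sound: a paired t-test with d_z = 0.65 and two-sided 5% gives power 0.809 at n=21, 0.912 at n=28 and 0.931 at n=30, in line with section 17.1.

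**2. The outcomes side by side.**

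| Outcome | Comparison with placebo | Conditional on FC result |
|---|---|---|
| FC | yes (4.0, 17.1) | no |
| Behaviour | yes (4.0, 17.1) | no |
| Side effects | none written | yes, more than one dose must pass |

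**3. How often would the comparison not run?** Inputs: a 20-point separation with d_z = 0.65, and n = 30 (section 17.1).
- SD = 20/0.65 = 30.77; SE = 30.77/√30 = 5.62 points.
- A dose passes if its estimate is at least 20. On one FC measure, P(pass) = 1 − Φ((20 − δ)/5.62): 0.04 for a true effect δ = 10, 0.19 for 15, 0.50 for 20 and 0.81 for 25.
- Section 4.0 lets either the right or the left ventral striatum meet the criterion, so both rules were simulated.
- Assumed, not in the documents: correlation 0.5-0.7 between dose estimates, correlation 0.3-0.7 between sides, and equal true effects on both sides.

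| True effects at 150/300/450 (points) | Fewer than two pass, one FC measure | Fewer than two pass, either side |
|---|---|---|
| 25/25/25 | 15-17% | 3-8% |
| 20/20/20 | 50% | 26-36% |
| 10/15/20 | 82-84% | 69-75% |
| 0/10/20 | 96-97% | 93-94% |

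The 50% is what symmetry gives when every true effect sits exactly on the cut-off.

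**4. What an uncontrolled rate can say.** Table 1 expects insomnia in about 10% in the first week: 3 of 30 patients, exact 95% interval 2.1% to 26.5%. The documents give no placebo-week rate. If it were 0%, 5% or 10%, the part due to the drug would be 10, 5 or 0 points: all, half or none of those events. A dose-to-dose comparison looks the same in all three cases.

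**5. Dose and time.** Doses rise weekly in a fixed order. In the study of older adults cited in section 5.0, nausea fell from 19.4% in week 1 to 9.1% in week 3 while the dose rose, a drop of 19.4 − 9.1 = 10.3 points. A dose-to-dose comparison cannot tell adaptation from a dose effect.

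**6. Precision of a placebo comparison.** For rates p_L and p_P in the same n = 30 patients, half-width = 1.96 × √{[p10 + p01 − (p10 − p01)²]/30}, where p10 and p01 are the probabilities of an event on L-DOPA only and on placebo only. Take p_L = 20-30% (nausea in the first days, Table 1), with assumed p_P = 3-10% and within-patient correlation 0-0.3.
- Example: p_L = 0.20, p_P = 0.10, correlation 0 gives p10 = 0.18, p01 = 0.08, and 1.96 × √[(0.26 − 0.01)/30] = 0.179.
- Over the range, leaving out the infeasible combination (30%, 3%, correlation 0.3), the half-width is about 14 to 20 points.
- Exact McNemar power is about 0.10-0.40 at p_L = 20% and 0.36-0.77 at 30%. This supports estimation rather than testing.

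**The case against.** The strongest reply is that the quoted sentence is a dose-ranking step and does that job without placebo. Within the same patients a common placebo rate cancels: (p_450 − p_P) − (p_150 − p_P) = p_450 − p_150. This stands. A reader might infer that the ranking step is invalid for want of a control, and the documents do not support that. The gap is that nothing else addresses the hypothesis.

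A reader might also infer that tolerability will go unanalysed altogether. That is too strong. Section 2.0 says it will be assessed, events are coded and judged for relatedness in a blinded study, section 17.3 promises descriptive statistics in general terms, and section 18.0 gives the DSMB annual adverse-event reports. The analysis is unspecified rather than excluded. Still, none of these names a comparator, and the DSMB's annual report to the IRB does not disclose treatment arm by default.

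A third tempting reading is that the comparison will probably never run. The either-side rule and true effects above 20 points, which section 17.1 treats as the floor of the expected separation, bring the chance down to a few percent.

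On severity, no figure in the documents shows a dose with fewer but worse events, and Table 1 anticipates mild ones. That harm is possible but not demonstrated. Lastly, the hypothesis is exploratory and n=30 gives little precision. Both are true, and both argue for a modest descriptive analysis rather than none.

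**Conclusion.** The point holds in limited form. A stated exploratory hypothesis about all doses has no analysis of its own. The one written comparison is conditional on FC, runs among L-DOPA doses only and ignores recorded severity, and the placebo period used for FC and behaviour is left unused for side effects. This follows from the text and needs no assumption. The chance that the comparison does not run ranges from about 3% to 97% over the scenarios above. It rests on assumed correlations and true effects and should be quoted only as that range. The insomnia illustration rests on assumed background rates and does not estimate harm in this trial. The matter should be put right, but it does not threaten the primary FC objective.

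**What to change.** Keep the dose-selection step in sections 4.0 and 17.1, and show moderate-or-worse events next to the counts when passing doses are compared. Add to section 17.1 a tolerability analysis that does not depend on the FC result:

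- For every treated patient, assign each adverse event by its recorded start date to placebo, 150, 300 or 450 mg/day. Give washout or de-escalation days (mentioned in sections 6.1 and 6.5) a separate category so that they are not counted as placebo.
- By condition, report the percent with any event, the percent with any moderate-or-worse event, and events per week.
- For each dose, give the within-person L-DOPA-minus-placebo difference with a 95% confidence interval as a descriptive estimate. State how many patients contribute, since those who stop early may lack one of the two conditions.
- Say plainly that dose is confounded with time on drug because escalation is fixed. The placebo comparison does not remove this.
- Summarise the dyskinesia review in the same way, and vital signs where they were measured in person.

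The cost is a paragraph of plan text and a few tables from data already collected, with no extra patients or visits. The downside is the wide intervals shown above. No dose or clinical rule is proposed.
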